### 16.1.1 PROBABILITY FOR DEMONSTRATING SEROCONVERSION CRITERIA FOR LICENSURE

For the 18-45 year old cohort, if the true seroconversion response to each strain is  $\geq 49\%$ , then there is 91% probability that the point estimate for seroconversion to all three strains will be  $\geq 40\%$ .

Likewise, if the true seroconversion response to each strain is  $\geq 60\%$ , then there is 92% probability that the lower bound of the exact 95% CI for seroconversion to all strains will be  $\geq 40\%$ . For the older age cohort (46-60 years old), if the true seroconversion response to each strain is  $\geq 39\%$ , then there is 93% probability that the point estimate for seroconversion to all three strains will be  $\geq 30\%$ . Given that the lowest seroconversion response in the IVAC Phase 1 trial was to B viral strain at 76.7% (95% CI, 57.7-90.1), there is high probability (Table 5) of demonstrating age group specific seroconversion requirement with a sample size of 100 evaluable participants per age group who received the study vaccine.

Table 5: Probability of demonstrating seroconversion response to all 3 viral strains by age groups and assumed true response to each viral strain.

Age group (point estimate response)	True response		
	Probability > 90%	Probability > 95%	Probability > 99%
18-45 ( $\geq 40\%$ )	$\geq 49\%$	$\geq 51\%$	$\geq 54\%$
46- 60 ( $\geq 30\%$ )	$\geq 39\%$	$\geq 40\%$	$\geq 43\%$

Document: \\EEDC-NAS01A\Biosdata\Path\IVACFLU-S\IYA06804\Biostatistics  
Documentation\SAP\IVACFLU-S-0203\_SAP\_Draft v1.0

Author: [name]

Version Number:

1.0

Version Date:

[11AUG2017]

Template No: CS\_TP\_BS016 Revision 4  
Effective Date: 01Apr2016

Reference: CS\_WI\_BS005

## 16.1.2 PROBABILITY FOR DEMONSTRATING SEROPROTECTION CRITERIA FOR LICENSURE

For the 18-45 year old cohort there is 92% probability that the point estimate for seroprotection to all three strains will be  $\geq 70\%$  if the true response to each strain is  $\geq 78\%$ . Likewise if the true response to each strain is  $\geq 87\%$ , then there is 95% probability that the lower bound of the exact 95% CI for seroprotection to all strains will be  $\geq 70\%$ . In the older age cohort (46-60 years old), if the true seroprotection response to each strain is  $\geq 69\%$ , then there is 93% probability that the point estimate for seroprotection to all three strains will be  $\geq 60\%$ . Given that the lowest seroprotection response in the IVAC Phase 1 trial was to B viral strain at 93.3% (95% CI 77.9; 99.2), there is high probability (Table 6) of demonstrating age group specific seroprotection requirement with a sample size of 100 evaluable participants per age group who received the study vaccine.

Table 6: Probability of demonstrating seroprotection response to all 3 viral strains by age groups and assumed true response to each viral strain.

Age group (point estimate response)	True response		
	Probability > 90%	Probability > 95%	Probability > 99%
18-45 ( $\geq 70\%$ )	$\geq 78\%$	$\geq 79\%$	$\geq 81\%$
46- 60 ( $\geq 60\%$ )	$\geq 69\%$	$\geq 70\%$	$\geq 72\%$

## 16.2 ANALYSIS OF IMMUNOGENICITY ENDPOINTS

### 16.2.1 PRIMARY IMMUNOGENICITY ENDPOINTS

- A. Number and percentage of subjects by age groups (18-45, 46-60) with seroconversion against each of the 3 vaccine antigens post-vaccination. Seroconversion is defined as a serum HAI antibody titer meeting the following criteria:
  - pre-vaccination titer  $< 1:10$  and a post-vaccination titer measured on Day 22 of  $\geq 1:40$  or
  - pre-vaccination titer  $\geq 1:10$  and at least a four-fold increase in post vaccination titer measured on Day 22
- B. Number and percentage of subjects by age groups (18-45, 46-60) with seroprotection, defined as a HAI antibody titer  $\geq 1:40$  to each of the 3 vaccine antigens measured on Day 22 post vaccination
- C. Geometric mean titers (GMTs) of serum HAI antibodies pre- (Day 1) and post vaccination (Day 22) by age groups (18-45, 46-60) for each of the 3 vaccine antigens
- D. Geometric mean fold rises (GMFRs) of serum HAI antibodies (post vaccination/prevaccination) by age groups (18-45, 46-60) for each of the 3 vaccine antigens

Document:	\\EEDC-NAS01A\Biosdata\Path\IVACFLU-S\IYA06804\Biostatistics		
	Documentation\SAP\IVACFLU-S-0203_SAP_Draft v1.0		
Author:	[name]	Version Number:	1.0
		Version Date:	[11AUG2017]
Template No:	CS_TP_BS016 Revision 4	Reference:	CS_WI_BS005
Effective Date:	01Apr2016		

## 16.2.2 SECONDARY IMMUNOGENICITY ENDPOINTS

- A. Number and percentage of subjects by age groups (18-45, 46-60) who develop at least a four-fold increase in HAI antibody titer to each of the vaccine antigens post vaccination measured on Day 22 by pre-vaccination HAI antibody titer of  $<1:10$  or  $\geq 1:10$ .
- B. Geometric mean titers (GMTs) of serum HAI antibodies pre- (Day 1) and post vaccination (Day 22) by age groups (18-45, 46-60) for each of the 3 vaccine antigens by prevaccination HAI antibody titer of  $<1:10$  or  $\geq 1:10$ .
- C. Geometric mean fold rises (GMFRs) of serum HAI antibodies (post vaccination/prevaccination) by age groups (18-45, 46-60) for each of the 3 vaccine antigens by prevaccination HAI antibody titer of  $<1:10$  or  $\geq 1:10$ .

The following endpoints will be analyzed by age group:

1. For each treatment group, the number and percentage of subjects with a serum HAI antibody titer  $\geq 1:40$  to each of the 3 vaccine components measured on Day 22 post vaccination, will be presented along with two-sided exact 95% CIs using Clopper-Pearson method.
2. For each treatment group, the number and percentage of subjects with seroconversion against each of the 3 vaccine antigens post-vaccination will be presented along with two-sided exact 95% CIs using Clopper-Pearson method.
3. GMTs of serum HAI antibodies for each of the 3 antigens will be summarized at each time point (Day 1 and Day 22) by treatment group along with the corresponding two-sided 95% CIs, by exponentiating the corresponding log-transformed means and their 95% CIs.
4. GMFRs of serum (HAI) antibodies (post-vaccination / pre-vaccination) for each of the 3 antigens will be summarized by treatment group along with the corresponding two-sided 95% CIs, by exponentiating the corresponding difference in log-transformed means between post-vaccination and pre-vaccination antibodies and their 95% CIs obtained via paired t-test method.

The following endpoints will be analyzed by age group and pre-vaccination HAI antibody titer of  $<1:10$  or  $\geq 1:10$ :

1. For each treatment group, the number and percentage of subjects who develop at least a four-fold increase in HAI antibody titer to each of the 3 vaccine antigens measured on Day 22 post vaccination, will be presented along with two-sided exact 95% CIs using Clopper-Pearson method. (Please refer to [Appendix 2](#) for sample SAS code for 95% confidence interval for single proportion using Exact Clopper-Pearson method).
2. GMTs of serum HAI antibodies for each of the 3 antigens will be summarized at each time point (Day 1 and Day 22) by treatment group along with the corresponding two-sided 95% CIs, by exponentiating the corresponding log-transformed means and their 95% CIs.

---

Document:	\\EEDC-NAS01A\Biosdata\Path\IVACFLU-S\IYA06804\Biostatistics		
	Documentation\SAP\IVACFLU-S-0203_SAP_Draft v1.0		
Author:	[name]	Version Number:	1.0
		Version Date:	[11AUG2017]
Template No:	CS_TP_BS016 Revision 4	Reference:	CS_WI_BS005
Effective Date:	01Apr2016		

3. GMFRs of serum (HAI) antibodies (post-vaccination / pre-vaccination) for each of the 3 antigens will be summarized by treatment group along with the corresponding two-sided 95% CIs, by exponentiating the corresponding difference in log-transformed means between post-vaccination and pre-vaccination antibodies and their 95% CIs obtained via paired t-test method.

Subject wise listing will be generated.

Graphical representation of the data will be as follows:

1. Geometric mean HAI titer for each of the 3 antigens at Days 1 and 22 will be plotted by vaccine group separately for each age group.
2. Reverse Cumulative Distribution (RCD) plot will show reverse cumulative percentages for HAI titer for each of the 3 antigens at Day 1 and Day 22 by vaccine group and by age group.

The immunogenicity analyses will be performed using PP population.

All immunogenicity analyses will also be conducted using FA population as supportive analyses.

### 16.3 VARIABLES & DERIVATIONS

Titers below the limit of quantification (i.e. below the starting dilution of assay reported as “< 10”) will be set to half that limit (i.e.  $10/2 = 5$ ). If a titer is reported as greater or equal to the upper limit of the assay, it will be set to that limit.

Fold increase (rise) [FI]:

If “vpre” is a subject’s pre-vaccination (baseline) immunogenicity value and “vpost” the post-vaccination value, then the “fold increase (rise)” [FI] will be calculated as:

$$FI = vpost / vpre$$

Seroprotection:

Taking influenza as an example, the threshold is an anti-HA antibody level of 40, and subjects with HAI antibody titre  $\geq 40$  are said to be seroprotected for influenza.

Seroconversion:

Seroconversion is defined as

- pre-vaccination titer  $< 1:10$  and a post-vaccination titer measured on Day 22 of  $\geq 1:40$ ; or
- pre-vaccination titer  $\geq 1:10$  and at least a four-fold increase in post vaccination measured on Day 22

i.e. subjects with an HAI antibody titer  $< 10$  and  $\geq 40$  before vaccination and post vaccination i.e., on Day 22 respectively; or

---

Document:	\\EEDC-NAS01A\Biosdata\Path\IVACFLU-S\IYA06804\Biostatistics		
	Documentation\SAP\IVACFLU-S-0203_SAP_Draft v1.0		
Author:	[name]	Version Number:	1.0
		Version Date:	[11AUG2017]
Template No:	CS_TP_BS016 Revision 4	Reference:	CS_WI_BS005
Effective Date:	01Apr2016		

an HAI antibody titer  $\geq 10$  and at least a four-fold increase in post vaccination measured on Day 22 i.e., FI  $\geq 4$

## 17. SAFETY OUTCOMES

### 17.1 STATISTICAL CONSIDERATIONS:

Null hypothesis ( $H_0$ ):

A single dose of seasonal trivalent inactivated split virion influenza vaccine (IVACFLU-S) is not safe and well tolerated in adults 18 to 60 years of age.

Alternative hypothesis ( $H_1$ ):

A single dose of seasonal trivalent inactivated split virion influenza vaccine (IVACFLU-S) is safe and well tolerated in adults 18 to 60 years of age.

The total sample size for Phase 2 and Phase 3 combined will be 888 subjects. With subjects randomized to IVACFLU-S or placebo at a randomization ratio of 5:1, there will be 740 subjects randomized to IVACFLU-S arm in the phase 2/3 study. Accounting for a 5% dropout rate, there would be at least 700 evaluable participants for safety analysis. If no vaccine-related serious adverse events are observed in 700 vaccine recipients, the study would be able to exclude events occurring at approximately 0.43% based on the upper bound of the one sided 95% Confidence Interval (CI) using the Clopper-Pearson method.

The probability of observing at least one vaccine-related serious adverse event in 700 subjects is 90 % and >95% if the true rate of such events is 0.33 % and 0.43% respectively. The precision of the estimate of AEs judged to be related to IVACFLU-S as bounded by 95% CI is presented in Table 7.

Table 7: Exact 95% Confidence Intervals around Potential Number of Study Related Adverse Events

Sample size	Number of events	2-sided exact 95% CI
700	0	[0, 0.52*]
	1	[<0.01, 0.79]
	2	[0.03, 1.02]
	3	[0.08, 1.24]
	5	[0.23, 1.65]

\*one sided, 97.5% CI

Document: \\EEDC-NAS01A\Biosdata\Path\IVACFLU-S\IYA06804\Biostatistics  
Documentation\SAP\IVACFLU-S-0203\_SAP\_Draft v1.0

Author: [name]

Version Number:

1.0

Version Date:

[11AUG2017]

Template No: CS\_TP\_BS016 Revision 4  
Effective Date: 01Apr2016

Reference: CS\_WI\_BS005

However, the full analysis population will be used for safety analysis, not the assumed number of 700 evaluable subjects.

## 17.2 ANALYSIS OF SAFETY ENDPOINTS:

The safety profile of IVACFLU-S will be evaluated by the number and proportion of subjects experiencing AEs by severity relatedness to vaccination in the following four categories for all subjects and by age group (solicited AEs will be considered related to study product):

- A. Solicited local adverse events, including redness / erythema, swelling / induration, pain within 30 minutes of vaccination and over a 7-day period (Days 1-7) post-vaccination.
- B. Solicited systemic adverse events, including fever, fatigue, malaise, muscle aches, joint aches, chills, nausea, vomiting, and headache within 30 minutes of vaccination and over a 7-day period (Days 1-7) post-vaccination.
- C. Unsolicited AEs occurring within 21 days post vaccination.
- D. Serious Adverse Events occurring during the entire study period (Days 1 to 91).

### 17.2.1 SOLICITED LOCAL AND SYSTEMIC ADVERSE EVENTS

Solicited adverse events are pre-specified local and systemic adverse events that are common or known to be associated with vaccination that are actively monitored as indicators of vaccine reactogenicity. Investigators will not be required to assess causality of solicited adverse events if the onset is during the solicitation periods. If a solicited adverse event progresses beyond the solicited period, it will continue to be reported as a solicited adverse event. If the solicited adverse event occurs after the solicitation period it will be reported as an unsolicited AE.

Any solicited local or systemic reactogenicity that occurs during the 5-day period post-injection is automatically regarded as related.

Solicited local and systemic AEs will be assessed by study staff 30 minutes after vaccination then daily for 7 days by the subjects.

- Solicited local adverse event (at site of injection):
  - Erythema / redness – based on size in cm
  - Swelling / induration (hardness at site of injection ) – based on size in cm
  - Pain
- Systemic Reactions:
  - Fever--Body temperature (measured in degrees Celsius)
  - Fatigue/malaise
  - Generalized muscle aches
  - Joint aches
  - Chills

---

Document: \\EEDC-NAS01A\Biosdata\Path\IVACFLU-S\IYA06804\Biostatistics  
Documentation\SAP\IVACFLU-S-0203\_SAP\_Draft v1.0

Author: [name]

Version Number:

1.0

Version Date:

[11AUG2017]

Template No: CS\_TP\_BS016 Revision 4  
Effective Date: 01Apr2016

Reference: CS\_WI\_BS005

- Nausea
- Vomiting
- Headache

Solicited local and systemic adverse events will be graded by a Principal Investigator (PI) using a standardized data collection instrument. Grading will use predefined scales based on functional assessment or magnitude of reaction, where available. Where grading scales are not provided, the reaction will be graded for severity based on interference with subject functionality, as for all other AEs. Severity of redness, swelling and induration at the injection site will always be graded based on the size. Temperature will be graded according to the following criteria:

- Ungradable
- Grade 1= '38.0 - <38.6°C'
- Grade 2= '38.6 – <39.3°C'
- Grade 3= '39.3 – <40.0°C'
- Grade 4= '≥ 40.0°C'

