### **8.2.2 Seventh Day after Injection (Day 8 ± 1)**

1. Study staff will confirm participant identity.
2. Study staff will review the participant Diary Card and interim history with the participant and inquire about any new medical events since medical histories were last updated. Any AEs that have occurred and meet reporting requirements, will be recorded in the appropriate section(s) of the CRF. Diary Card information will be entered into the database.
3. The participant will have temperature, pulse rate, and blood pressure recorded. A study clinician will perform a targeted (symptom based) physical examination and record the information Results will be reviewed by study staff and with the participant.
4. The participant will be instructed to inform the investigator as soon as possible if he/she experiences an AE requiring medical care and to seek medical care as appropriate. If the participant visits a health care provider, the participant should be sure to inform the

health care provider of participation in this study and give the health care provider the contact information for the investigator.

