#### INSTRUCTIONS

1. Take your temperature by mouth each day using the thermometer we gave you.

- Start taking your temperature later today.
- Take it around the same time each day.
- Wait 15 minutes if you had a hot or cold drink.
- Insert the thermometer into your mouth under your tongue. Close your mouth.
- Wait for the beep or other indication that the temperature is ready.
- Write the temperature in the space on the Diary Card. If you take your temperature more than once during the day, write the highest temperature for the day on the Diary Card.

2. Each day, look at your arm where you received the injection.

- Check for redness and swelling. Touch your arm and feel for hardness at the injection site.
- If you do not find anything, check “None” on the diary card for the day.
- If you see or feel something, place a mark with a pen on either side of the area. Measure the widest part of it with the ruler we have given you.
- Record your measurement on the Diary Card. If you do more than one measurement during the day, record the largest measurement for each day on the Diary Card.
- Example: This person had redness at the injection site. They put dots with a pen at the widest points of the redness and measured it. It measured 2.4 cm. They wrote 2.4 cm on the Diary Card for that day.

3. Severity of symptoms:

- None: I did not have any discomfort
- Mild: I only had minor discomfort. I did my usual activities
- Moderate: I noticed the symptom. It bothered me enough that I did not do as much as I usually do
- Severe: I really noticed the symptom. It kept me from doing many of the things I wanted or needed to do

4. Please contact the study site using the number below if you have any questions:

Participant ID | | | | |

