**TAKE-HOME DIARY CARD**  
**LOCAL REACTIONS within 7 days post-vaccination**

	Evening Day 1 (Day of vaccination) ___/___/2017	Day 2 ___/___/2017	Day 3 ___/___/2017	Day 4 ___/___/2017	Day 5 ___/___/2017	Day 6 ___/___/2017	Day 7 ___/___/2017
Redness at injection site	 None  Yes, measurement: ___ mm						
Swelling at injection site	 None  Yes, measurement: ___ mm						
Hardness at injection site	 None  Yes, measurement: ___ mm						

Participant ID

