## 2.4 ASSESSMENT OF OBJECTIVES

### 2.4.1 ENDPOINT VARIABLES

- Solicited local adverse events (at site of injection):
  - Erythema / redness - based on size in cm
  - Swelling / induration (hardness at site of injection) - based on size in cm
  - Pain

---

Document: \\EEDC-NAS01A\Biosdata\Path\IVACFLU-S\IYA06804\Biostatistics  
Documentation\SAP\IVACFLU-S-0203\_SAP\_Draft v1.0

Author: [name]

Version Number:

1.0

Version Date:

[11AUG2017]

Template No: CS\_TP\_BS016 Revision 4  
Effective Date: 01Apr2016

Reference: CS\_WI\_BS005

- Solicited systemic adverse events:
  - Fever-Body temperature
  - Fatigue/malaise
  - Generalized muscle aches
  - Joint aches
  - Chills
  - Nausea
  - Vomiting
  - Headache
- Unsolicited adverse events
- Serious adverse events
- Seroprotection
- Seroconversion
- Geometric mean titers (GMT) of serum HAI antibodies
- Geometric mean fold rises (GMFR) of serum HAI antibodies

### 2.4.1.1 PRIMARY SAFETY ENDPOINTS, PHASE 2 AND 3

The number and proportion of participants reporting the following events:

- A. Solicited local adverse events, including redness / erythema, swelling / induration, pain within 30 minutes of vaccination and over a 7-day period (Days 1-7) post-vaccination.
- B. Solicited systemic adverse events, including fever, fatigue/malaise, muscle aches, joint aches, chills, nausea, vomiting, and headache within 30 minutes of vaccination and over a 7-day period (Days 1-7) post-vaccination.
- C. Unsolicited Adverse Events (AEs) occurring within 21 days post vaccination.
- D. Serious Adverse Events (SAEs) occurring during the entire study period (Days 1-91).

### 2.4.1.2 PRIMARY IMMUNOGENICITY ENDPOINTS, PHASE 3

- A. Number and percentage of participants by age groups (18-45, 46-60) with seroconversion against each of the 3 vaccine antigens post-vaccination. Seroconversion is defined as a serum HAI antibody titer meeting the following criteria:
  - pre-vaccination titer <1:10 and a post-vaccination titer measured on Day 22 of  $\geq 1:40$  or
  - pre-vaccination titer  $\geq 1:10$  and at least a four-fold increase in post vaccination measured on Day 22

---

Document:	\\EEDC-NAS01A\Biosdata\Path\IVACFLU-S\IYA06804\Biostatistics		
	Documentation\SAP\IVACFLU-S-0203_SAP_Draft v1.0		
Author:	[name]	Version Number:	1.0
		Version Date:	[11AUG2017]
Template No:	CS_TP_BS016 Revision 4	Reference:	CS_WI_BS005
Effective Date:	01Apr2016		

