### 17.2.1.1 PRESENTATION OF 30-MINUTE SOLICITED LOCAL AND SYSTEMIC REACTOGENICITY

The following will be presented for the FA population:

1. Subject-wise listing of 30-minute solicited local and systemic reactogenicity will be generated separately.
2. Summary of 30-minute solicited local and systemic reactogenicity will be provided separately as follows:
  - 
  - Count and percentages of participants experiencing each reaction or event, or at least one reaction or event will be calculated along with two-sided exact 95% CIs using Clopper-Pearson method (refer [Appendix 2](#)) for each treatment group, and by age group.
  - Fisher's exact test (refer [Appendix 3](#)) or Cochran-Mantel-Haenszel test (refer [Appendix 4](#)) will be used to compare the proportion of participants between the two treatment groups.
3. Descriptive summary (as described for continuous variables in [Section 6](#)) of the size of the solicited local reactions captured in 30-minute reactogenicity page of the eCRF will be presented by vaccine and placebo.
4. In addition, for all Solicited Local and Systemic Adverse Events, the following will be summarised by severity:
  - Counts of all events will be reported and summarized, as "any local AE" or "any systemic AE".

---

Document:	\\EEDC-NAS01A\Biosdata\Path\IVACFLU-S\IYA06804\Biostatistics		
	Documentation\SAP\IVACFLU-S-0203_SAP_Draft v1.0		
Author:	[name]	Version Number:	1.0
		Version Date:	[11AUG2017]
Template No:	CS_TP_BS016 Revision 4	Reference:	CS_WI_BS005
Effective Date:	01Apr2016		

- Percentages of subjects experiencing each reaction or event, at least one reaction or event will be calculated. This will be generated separately i.e., one output for Body temperature (Oral) and one output for all other adverse events, as the severity grades will be as follows:
  - Body temperature (Oral):
    - Ungradable
    - Grade 1= '38.0 - <38.6°C'
    - Grade 2= '38.6 – <39.3°C'
    - Grade 3=' 39.3 – <40.0°C'
    - Grade 4=' ≥ 40.0°C'
  - For local and systemic adverse events:
    - None
    - Mild
    - Moderate
    - Severe
    - Potentially Life Threatening

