### 17.2.1.2 PRESENTATION OF SOLICITED LOCAL AND SYSTEMIC ADVERSE EVENTS

The following will be presented for the FA population:

1. Subject-wise listing of solicited local and systemic adverse events will be generated separately.
2. Summary of solicited local and systemic adverse events will be provided separately as follows:
  - Counts and percentages of subjects experiencing each reaction or event, at least one reaction or event will be calculated.
  - Number of events for each reaction or event will also be displayed.
  - Event will be counted only one time if occurred on consecutive days.

Percentages of participants experiencing each reaction or event, or at least one reaction or event will be calculated along with two-sided exact 95% CIs using Clopper-Pearson method (refer [Appendix 2](#)) for each treatment group and by age group. Fisher's exact test (refer [Appendix 3](#)) or Cochran-Mantel-Haenszel test (refer [Appendix 4](#)) will be used to compare the proportion of participants between the two treatment groups.

3. Summary of solicited local and systemic adverse events, as described in the above point 2 will be repeated i.e., summarized by day:

---

Document:	\\EEDC-NAS01A\Biosdata\Path\IVACFLU-S\IYA06804\Biostatistics		
	Documentation\SAP\IVACFLU-S-0203_SAP_Draft v1.0		
Author:	[name]	Version Number:	1.0
		Version Date:	[11AUG2017]
Template No:	CS_TP_BS016 Revision 4	Reference:	CS_WI_BS005
Effective Date:	01Apr2016		

- Counts and percentages of subjects experiencing each reaction or event, at least one reaction or event will be calculated.
  - Number of events for each reaction or event will also be displayed.
4. Descriptive summary (as described for continuous variables in [Section 6](#)) of the size of the solicited local reactions captured as per the eCRF will be presented by vaccine and placebo.

In addition, for all Solicited Local and Systemic Adverse Events the following will be summarised by maximum severity until resolution:

- Counts of all events will be reported and summarized, as “any local AE” or “any systemic AE”.
- Percentages of subjects experiencing each reaction or event, at least one reaction or event will be calculated. This will be generated separately i.e., one output for Body temperature (Oral) and one output for all other adverse events, as the severity grades will be as follows:
  - Body temperature (Oral):
    - Ungradable
    - Grade 1= ‘38.0 - <38.6°C’
    - Grade 2= ‘38.6 – <39.3°C’

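### The Day 1–7 eCRF holds no size for redness, swelling or hardness and no code for a reaction present but under 2.5 cm, so the SAP's size-based grading and Day 1–7 size summary cannot be produced from the database

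*Combined protocol and SAP*

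**What the plan says.** The SAP ties these signs to size. Section 2.4.1 lists the redness variable as "Erythema / redness - based on size in cm" and treats swelling/induration the same way. Section 17.2.1 adds that "Severity of redness, swelling and induration at the injection site will always be graded based on the size". Two size summaries are planned. Item 3 of 17.2.1.1 covers the "size of the solicited local reactions captured in 30-minute reactogenicity page of the eCRF". Item 4 of 17.2.1.2, the section on the solicited events after the 30-minute check, is a descriptive summary "of the size of the solicited local reactions captured as per the eCRF will be presented by vaccine and placebo".

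On collection, the diary card has a box for redness, swelling and hardness on each of Days 1 to 7 that reads "Yes, measurement: ___ mm". Protocol 8.2.2, on the Day 8 visit, says that "Diary Card information will be entered into the database". Protocol Appendix A starts Grade 1 erythema at a diameter of 2.5 cm and uses the same scale for induration or swelling.

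**The concern.** The measurement is taken, and the SAP relies on it, but the form between the two does not carry it. Two things follow. A planned output has no source. And for small reactions, someone must choose a severity code without a visible rule, in a way that cannot be audited from the data.

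Solicited local events are a primary safety endpoint in both phases (protocol 3.2.1). Shell Table 14.3.2.1.1 gives redness and swelling their own Day 1–7 incidence rows with a p-value. What is at stake is the meaning of those rows, and whether they agree with the 30-minute data. The any-local-event row is less exposed, because pain and tenderness dominate it: 19/30 and 17/30 among Phase 1 vaccinees (protocol Table 3).

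**Working it through.** **Step 1: the forms side by side (redness, swelling, hardness/induration).**

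| Source | Size | Severity codes |
|---|---|---|
| Diary, Days 1–7 | mm box per sign per day | None, or a measurement |
| eCRF, 30-minute page | 3 fields in cm | None as a separate choice; Ungradable and Grades 1–4 beside the size |
| eCRF, Day 1–7 page | none (3 signs × 7 days = 21 severity items, text columns only) | 0 None, 1 Mild, 2 Moderate, 3 Severe, 4 Potentially Life Threatening |
| eCRF, ongoing after Day 7 | none | Grades 1–4 only |
| SAP local severity rows; shell 14.3.2.1.7, which 14.3.2.2.1 repeats | – | None to life threatening; no Ungradable row |

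Oral temperature for Days 1–7 is stored as a number, so the omission is specific to the local signs.

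**Step 2: the size summary.** Item 4 of 17.2.1.2 cannot simply mean the 30-minute sizes, because item 3 of 17.2.1.1 already covers them. The only size shell, Table 14.3.2.1.9, is for 30 minutes. Listing 16.2.7.1 shows centimetres at 30 minutes but a severity word on Day 1. The Day 1–7 summary has neither variable nor shell.

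**Step 3: one small reaction through the Day 1–7 page.** The diary's own worked example is redness: "It measured 2.4 cm. They wrote 2.4 cm on the Diary Card for that day". Since 2.4 < 2.5, it is below Grade 1. Short of leaving the item blank, the choices are:
- None. But the diary instruction that begins "If you do not find anything, check" keeps None for finding nothing.
- Mild. But that contradicts the 2.5 cm bound and grading by size.

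Appendix A does not settle it. Its between-grades rule needs two candidate grades, and its below-Grade-1 rule covers laboratory values only. The SAP's fallback to functional interference applies where there is no scale, and the next sentence says size always decides.

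The unit is also open. The example is in cm and the box in mm. Since 2.4 cm = 24 mm, a bare 2.4 in the box would be wrong by a factor of 10.

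**Step 4: how many participants.** The plan gives no figure to reproduce.

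Phase 1 vaccinees (protocol Table 3): swelling 1/30 and hardness 1/30 (3.3%, exact 95% CI 0.1–17.2%), both Moderate, with no redness row. Mild was 0/30, with an upper limit of 11.6%. That is compatible with 0 to 86 of 740 (0.1157 × 740 = 85.6). Phase 1 may share the coding question.

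Illustration only, from protocol Table 11 (another vaccine), whose footnotes put Grade 2 at 2.5 to <5 cm and Grade 3 at ≥5 cm. Rate under 2.5 cm = Any − Grade 2 − Grade 3:

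| Sign | Any | ≥2.5 cm | <2.5 cm | Share <2.5 cm |
|---|---|---|---|---|
| Erythema | 13.2% | 2.1 + 0.9 = 3.0% | 10.2% | 77% |
| Induration | 10.0% | 2.3 + 0.5 = 2.8% | 7.2% | 72% |
| Swelling | 8.4% | 2.1 + 0.9 = 3.0% | 5.4% | 64% |

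Applied to 740 vaccine recipients, with exact 95% CIs:

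| Sign | Small reactions coded None | Small reactions coded Mild |
|---|---|---|
| Redness | 22 (3.0%, 1.9–4.5) | 98 (13.2%, 10.9–15.9) |
| Induration | 21 (2.8%, 1.8–4.3) | 74 (10.0%, 7.9–12.4) |
| Swelling | 22 (3.0%, 1.9–4.5) | 62 (8.4%, 6.5–10.6) |

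Without Table 11: if 0.5% to 10% of recipients have only a reaction under 2.5 cm, then 4 to 74 of 740 change category.

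**The case against.** The strongest reply is that the codes work as they are. The daily list starts at 0, severity goes by size, and anything below the scale is naturally a 0. The documents use that convention for temperature: Phase 1 calls normal temperatures Grade 0, and Listing 16.2.7.3 prints Grade 0. This reading is plausible, but it is not written down for local signs. It would also count a measured reaction as no event.

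Second, item 4 limits itself to what the eCRF captures, the protocol's endpoints are numbers and proportions, and 8.2.2 does not say that every raw measurement is entered. That is fair: the missing summary alone can be cured by one sentence. It does not cure the coding gap.

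Third, a rule may sit in the eCRF completion guidelines (protocol Appendix B) or in MOP 04 (cited for grading in the vital-signs criteria), neither of which is supplied. That stands, and lowers confidence on the coding rule.

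A reader might also infer more than the documents support:
- That there is no code below Grade 1, or no size data at all. The daily list has 0 None, and the sizes remain on the paper diaries.
- That the 30-minute Ungradable code means under 2.5 cm. It is never defined, and it is offered for temperature and blood pressure too.
- That the arms are biased against each other or power is lost. Grading is blinded, so no bias between arms is expected, and nothing here quantifies power.
- That about three quarters of this vaccine's redness is at risk. That share belongs to another product.

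**Conclusion.** The point holds in a limited form and is worth fixing before unblinding. The Day 1–7 size summary has no eCRF variable or shell. Grading by size cannot be derived or verified from the database. A measured reaction under 2.5 cm is either lost from the Day 1–7 incidence or graded against Appendix A. At 30 minutes, an Ungradable local reaction has no row in the SAP or shell severity tables.

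Confidence is high on the missing size field and table row. It is medium on the coding rule, because unseen guidelines may contain one. The effect on this product's rates is unknown, and the Table 11 counts only show that the choice of rule could matter. The required yes/no item on any local reaction still records that something was reported, but not which sign.

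**What to change.** - Enter the diary sizes, with mm or cm confirmed, wherever a reaction was measured; derive the grade from size; and add a Day 1–7 size shell. If sizes are not entered, limit item 4 of SAP 17.2.1.2 to 30 minutes.
- Before unblinding, state that a measured reaction under 2.5 cm counts as present in the incidence, and show the rate at 2.5 cm or more beside it. If the completion guidelines or MOP 04 already hold a rule, quote it in the SAP.
- Add an 'ungradable / <2.5 cm' row to the 30-minute and Day 1–7 local severity tables.
- Reconcile SAP 17.2.1, where size always decides, with Appendix A, which also grades on symptoms and complications.

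Cost: one more eCRF version (the current one is version 4), up to 21 size entries per participant but only where a reaction was measured, and SAP and shell wording. Participants do nothing new. Reported redness and swelling rates may rise. The cheapest acceptable version is one sentence limiting item 4 plus one stated or cited rule for reactions under 2.5 cm. It leaves size-based grades uncheckable from the database.
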